Bilateral cataracts with corneal astigmatism in at least 1 eye of approximately 2.00 D to 3.00 D (higher-cylinder group) or approximately 1.00 D to 1.50 D (lower-cylinder group) based on the combination of preoperative keratometric cylinder, the expected effect of surgically-induced astigmatism (SIA), use of the optional posterior corneal astigmatism (PCA) algorithm and TECNIS Symfony Toric Calculator outcomes of ZXT300 or ZXT375 (higher-cylinder group) or ZXT150 (lower-cylinder group).

Number of subjects:Up to 634 subjects will be enrolled to achieve
bilateral implantation in approximately 506 subjects,
resulting in approximately 240 evaluable subjects in
the higher-cylinder group and 240 evaluable subjects
in the lower-cylinder group at 6 months

This is a bilateral study; both eyes must be implanted with a TECNIS Symfony IOL, either toric (Models ZXT150, ZXT225, ZXT300 or ZXT375) or non-toric (TECNIS Symfony Extended Range of Vision IOL, Model ZXR00). Each eye may have a different TECNIS Symfony IOL implanted, as determined by the surgeon and the TECNIS Symfony Toric IOL calculator; however, at least one eye must be implanted with either a Symfony Toric IOL Model ZXT150 (lower-cylinder group) or a Model ZXT300 or ZXT375 (higher-cylinder group) and the fellow eye must have the same or a lower toric power. The eye with the highest toric power IOL will determine the model group.

NOTE: No site may enroll more than 25% of the enrollment total.

Inclusion Criteria (all study criteria apply to each study eye unless otherwise indicated):

- Minimum 22 years of age
- Bilateral cataracts for which phacoemulsification extraction and posterior chamber IOL implantation have been planned
- Preoperative keratometric cylinder of:
 - Approximately 2.00 D to 3.00 D resulting in a calculated lens power (using the web-based TECNIS Symfony Toric IOL Calculator) that requires implantation of a ZXT300 or ZXT375 IOL in at least one eye for the subject to be eligible for the higher-cylinder group, or

- Approximately 1.00 D to 1.50 D resulting in a calculated lens power (using the web-based TECNIS Symfony Toric IOL Calculator) that requires implantation of a ZXT150 IOL in at least one eye for the subject to be eligible for the lower-cylinder group
- The eye with the higher toric power IOL will determine the model group
- The fellow eye must be the same or a lower toric power

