Other endpoints are individual visual symptom ratings included in the PRVSQ, rates of IOL repositioning procedures (secondary surgical intervention) due to IOL misalignment, rates of explants due to visual symptoms, distance visual acuities, mean percent reduction in absolute cylinder, mean refractive cylinder, mean refractive cylinder compared to the preoperatively-predicted cylinder, mean spherical equivalent, spherical equivalent compared to the preoperatively-predicted spherical equivalent, percent of eyes with cylinder and spherical equivalent (MRSE) within 0.50 D and within 1.00 D of the preoperatively-predicted spherical equivalent, rates of medical and/or lens findings, and rates of other adverse events. Preoperatively-predicted values will be based upon those generated from the TECNIS Symfony Toric IOL calculator.

DATA ANALYSIS:

The key time frame for analysis will be the 6-month visit. The first primary endpoint for this study will be the rate of bothersome visual symptoms,

The second primary endpoint will be the rate of those having a lot of difficulty with an activity due to halos, glare or starbursts as measured in the PRVSQ. The primary endpoint results will be compared between higher-cylinder toric IOL subjects and lower-cylinder toric control IOL subjects at the 6-month visit. The frequency, proportion and 95% Confidence Interval (CI) will be reported for higher-cylinder and lower-cylinder control subjects. This will be done for the higher-cylinder (ZXT300 and ZXT375) and lower-cylinder (ZXT150) groups.

Descriptive statistics will be used for reporting results. Visual acuity data will be reported by acuity line achieved. For questionnaire items, the frequency and proportion for each response will be reported. For refractive data, descriptive statistics will include mean, standard deviation, median, minimum and maximum and also the percent achieving absolute values within 0.50 D and 1.00 D of preoperatively-predicted values.

The frequency and proportion of primary and fellow eyes with adverse events or medical/lens findings will also be reported.

STUDY VISITS AND PROCEDURES:

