4. STUDY DESIGN

This study is a prospective, multicenter, bilateral, non-randomized, open-label, comparative, 6-month clinical study conducted at up to 50 sites in the USA. Subjects who meet the inclusion/exclusion criteria will be bilaterally implanted with Symfony IOLs, with either 1) Model ZXT300 or ZXT375 IOLs (higher-cylinder group), or 2) control Model ZXT150 (lower-cylinder control group) IOL, implanted in at least one eye, according to the TECNIS Symfony Toric IOL calculator. The fellow eye will be allowed to have any Symfony IOL implanted, according to the TECNIS Symfony Toric IOL calculator, provided it is the same or a lower toric power as the primary eye. The eye with the highest toric power IOL will determine the model group.

JUSTIFICATION OF STUDY DESIGN

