21.2 PRIMARY ENDPOINT

The primary endpoints are the rate of bothersome visual symptoms and the rate of reported difficulty with an activity due to visual symptoms at 6 months postoperative.

The first primary endpoint is the rate of bothersome visual symptoms,

. The second primary endpoint is the rate of reported difficulty with an activity due to one or more visual symptoms, determined by a "Yes" response to the question "Is there anything you have a lot of difficulty with, or do not do, because of [visual symptom]") at 6 months postoperative.

The frequency and proportion of subjects with bothersome visual symptoms for one or more visual symptoms, and the frequency and proportion of subjects reporting difficulty with an activity due to one or more visual symptoms will be reported along with the two-sided, 95% confidence interval at the 6-month visit.

Justification of Effect Size:

Using an assumed value of 20% for bothersome visual symptoms or difficulty with an activity due to visual symptoms, and a sample size of 240 evaluable subjects per group, a two-sided 95% confidence interval will estimate the observed rate of bothersome visual symptoms to within 4.2 percentage points.

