21.4 INTERIM REPORTS

21.5 SAMPLE SIZE CALCULATIONS

With a sample size of 240 subjects and assuming a 20% rate of bothersome visual symptoms or difficulty with an activity due to visual symptoms, a two-sided 95% confidence interval will estimate the observed rate of bothersome visual symptoms to within 4.2 percentage points.

[figure not shown]
To achieve 240 higher-cylinder group subjects and 240 lower-cylinder group subjects evaluable at 6 months, assuming an initial 20% screen-fail rate and a 5% lost-to-follow-up rate, up to 634 total subjects will be enrolled.

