## 4 POSTOPERATIVE ANALYSES – PRIMARY ENDPOINTS

There are two primary endpoints for this study, rate of bothersome visual symptoms and rate of difficulty with an activity due to the symptoms at 6-month postoperative.

The first primary endpoint is the rate of bothersome visual symptoms,

The second primary endpoint is the rate of reported difficulty with an activity due to one or more visual symptoms, determined by a

"Yes" response to the question "Is there anything you have a lot of difficulty with, or do not do, because of [visual symptom]") at 6 months postoperative.

The frequency and proportion of subjects with bothersome visual symptoms and the frequency and proportion of subjects reporting difficulty with an activity due to one or more visual symptoms will be reported along with the two-sided, 95% confidence interval at the 6-month visit.

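### The readable plan makes no allowance for site in the 95% intervals of the primary rates; simple binomial intervals would be too narrow if symptoms cluster within site

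*Protocol*

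**What the plan says.** The Data Analysis part of the Protocol Synopsis states: "The frequency, proportion and 95% Confidence Interval (CI) will be reported for higher-cylinder and lower-cylinder control subjects". SAP 4 repeats this for both primary endpoints, whose frequencies and proportions "will be reported along with the two-sided, 95% confidence interval at the 6-month visit". Neither document names the method for the interval.

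Precision is tied to the number of subjects. Protocol 21.2 speaks of "a sample size of 240 evaluable subjects per group, a two-sided 95% confidence interval". Protocol 21.5 starts from 240 subjects and an assumed 20% for either primary endpoint, and concludes that "a two-sided 95% confidence interval will estimate the observed rate of bothersome visual symptoms to within 4.2 percentage points". SAP 7 says the same. None of these places mentions a design effect or an intra-site correlation.

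On sites, Protocol 4 describes a "6-month clinical study conducted at up to 50 sites in the USA", and the Synopsis adds a cap: "No site may enroll more than 25% of the enrollment total". No minimum number of sites is readable. In the readable analysis text, site appears only in SAP 3.1, where enrolled subjects are counted by site. SAP Appendix I refers to the SAP text for inferential methods comparing the groups, but no such method is readable there. The objective in Protocol 1 and 6 is to learn the symptom rates in a wider population treated in routine practice.

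**The concern.** Subjects at one site share a surgeon and a way of working, and the protocol leaves much to each investigator. Examples are the surgeon's own standard technique (11.5), the preferred biometry method and estimated surgically induced astigmatism (11.3), and a personalised lens constant (note to Table 2). Site staff also review each completed questionnaire (11.6). The endpoints are self-reported and the study is open-label. Any of these could raise or lower reported halos, glare and starbursts for all subjects of a site together.

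If the aim is to speak about practice beyond the enrolled sites, variation between sites is part of the sampling error, and a simple binomial interval leaves it out. The interval would then look more precise than it is, the more so the more enrolment is concentrated. This point concerns the variance of each group's rate. It is separate from any imbalance of sites between the two lens groups.

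**Working it through.** **Inputs from the documents.** Rate p = 0.20 and n = 240 per group (Protocol 21.2 and 21.5, SAP 7); two-sided 95%, so z = 1.96; up to 50 sites (Protocol 4); at most 25% of enrolment from one site (Synopsis).

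**Assumed.** The ICC is not in the documents. I take 0.02 to 0.05 as the working range and show 0.01 and 0.10 around it. A site at the cap is taken to have the same mix of lens groups as the study, so it supplies 0.25 × 240 = 60 subjects per group.

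**Step 1: the plan's own figures.**
- Half-width under independence: 1.96 × √(0.20 × 0.80 / 240) = 1.96 × 2.582 = **5.06 points**. The stated 4.2 does not reproduce. Wilson gives 5.04 and Clopper-Pearson 5.25. A two-sided 90% interval gives 1.645 × 2.582 = 4.25, which is close to the stated value.
- Enrolment ("assuming an initial 20% screen-fail rate and a 5% lost-to-follow-up rate, up to 634 total subjects will be enrolled") does reproduce: 240/0.95 rounds up to 253 per group (506 in all), and 253/0.80 rounds up to 317 per group (634 in all). So the inflation covers screen failure and loss to follow-up and nothing else.
- The stated 4.2 is below the simple binomial value, and a design effect above 1 can only raise that value. The precision statement therefore shows no sign of an allowance for site.

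**Step 2: allowing for site.** With m_i subjects from site i in a group:
- m = Σm_i² / Σm_i
- DEFF = 1 + (m − 1) × ICC
- half-width = 5.06 × √DEFF
- coverage of the unadjusted interval = 2Φ(1.96/√DEFF) − 1

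For 50 equal sites, m = 240/50 = 4.8. For one site of 60 with 49 sites sharing 180, m = (60² + 180²/49)/240 = 17.76.

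| Site pattern | ICC | DEFF | Half-width (points) | Coverage of unadjusted interval |
|---|---|---|---|---|
| Any | 0 | 1.00 | 5.06 | 95% |
| 50 equal sites | 0.01 | 1.04 | 5.16 | 95% |
| 50 equal sites | 0.02 | 1.08 | 5.25 | 94% |
| 50 equal sites | 0.05 | 1.19 | 5.52 | 93% |
| 50 equal sites | 0.10 | 1.38 | 5.94 | 90% |
| One at 25%, 49 share the rest | 0.01 | 1.17 | 5.47 | 93% |
| One at 25%, 49 share the rest | 0.02 | 1.34 | 5.85 | 91% |
| One at 25%, 49 share the rest | 0.05 | 1.84 | 6.86 | 85% |
| One at 25%, 49 share the rest | 0.10 | 2.68 | 8.28 | 77% |

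A beta-binomial simulation of the second pattern (100,000 runs) gave coverage of 90% at ICC 0.02 and 84% at 0.05, slightly below the formula.

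**Step 3: extreme bound.** Four sites at 25% each give m = 60, DEFF 2.18 to 3.95, half-widths of 7.47 to 10.06 points and coverage of 82% to 68% for ICC 0.02 to 0.05.

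**The case against.** The strongest reply is that a reader might infer that the plan computes its intervals as if subjects were independent, and that they are certainly too narrow. The documents do not say so. No method is named, and independence is inferred from the precision statement and from silence. The silence has limits: SAP 2.1 breaks off after introducing the final report, no SAP section 6 is readable, Protocol 21.1 has a gap in its additional analyses, and Protocol 21.4 shows no text. An allowance for site there cannot be excluded. This stands, and the point is limited to the readable plan.

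Second, the size depends on an assumed ICC and on how enrolment falls. With 50 equal sites the effect is minor. The cap is a ceiling meant to limit concentration, not a planned share. This also stands. A reader might take the 68% coverage of the four-site case as the expected loss, but nothing in the documents plans for four sites. In that case robust variance is itself undependable: a t reference on 3 degrees of freedom (3.18 instead of 1.96) would give roughly 12 to 16 points.

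Third, the sponsor selects the surgeons (Protocol 9.1), so sites are not a random sample of practice, and a cluster-robust interval would not guarantee 95% coverage of a practice-wide rate. True, but it would still reflect variation between sites that the simple interval omits.

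Fourth, some shared influences are limited by design. Subjects complete the questionnaire themselves, and one web calculator guides lens choice. Reporting is also descriptive, with no readable decision threshold, and in a group difference shared site effects partly cancel where sites recruit to both groups. These points lower the stakes. They do not tell the reader how the interval will be computed.

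**Conclusion.** The concern holds as a gap in the readable plan: the intervals for the primary rates have no named method and no allowance for site. Whether that makes them too narrow depends on a positive ICC, which the documents neither give nor exclude.

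Under an assumed ICC of 0.02 to 0.05, allowing for site adds 0.19 to 0.46 points to the half-width with 50 equal sites, which is small. With one site at the cap it adds 0.79 to 1.80 points, which is material for an interval meant to convey precision. The four-site figures are only an outer bound.

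One error needs no assumption about sites. At the plan's own inputs the two-sided 95% half-width is 5.06 points, so the stated 4.2 is 0.86 points too small. That shortfall is larger than what clustering adds with 50 equal sites over the working ICC range. Both primary endpoints are counted per subject, so having two eyes per subject adds no further clustering to these rates.

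**What to change.** - **Protocol 21.2 and SAP 4:** name the interval method. Beside the simple binomial interval, report a site-robust 95% interval for each primary rate, for example from GEE clustered on site with a small-sample correction. Report the estimated ICC.
- **Any interval for the group difference:** use a method that accounts for site, and note that the interval may widen or narrow as a result.
- **Protocol 21.2 and 21.5, SAP 7:** replace 4.2 points with 5.06 under independence, and give the half-width for a stated ICC (for example 5.52 points at ICC 0.05 with 50 equal sites).

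The cost is plan wording and a few lines of code on data already held, with no added subjects or visits. The downside is somewhat wider intervals. If very few sites enrol, robust variance is unreliable; the plan should say so and show the rates by site in that case.

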2. BACKGROUND/INTRODUCTION

Amongst patients undergoing cataract surgery, approximately 35-41% of cataract patients have ≥ 0.75 diopter of corneal astigmatism, with 15%-20% having ≥ 1.5 D of corneal astigmatism.^{1,2} Although there are various modalities to reduce the amount of astigmatism during cataract surgery (e.g., limbal relaxing incisions, etc.), toric IOLs are now commonly used for correction of aphakia and pre-existing ocular astigmatism.

The TECNIS Symfony Extended Range of Vision IOLs were designed in response to a patient need for lenses that can provide good distance vision, improved intermediate and near vision compared to standard monofocal IOLs, and less dysphotopsia compared to a multifocal IOL. The Symfony IOLs utilize diffractive technology to mitigate the effects of presbyopia by providing an extended depth of focus, while keeping visual symptoms to a minimum and reducing chromatic aberration. In addition, the Symfony Toric IOLs include an anterior aspheric optic with a toric surface to correct for ocular astigmatism.

On July 15, 2016, JJSV received USA FDA approval (P980040/S065) for the TECNIS Symfony Extended Range of Vision IOL, Model ZXR00, and the TECNIS Symfony Toric Extended Range of Vision IOLs, Models ZXT150, ZXT225, ZXT300 and ZXT375, for the visual correction of aphakia and pre-existing corneal astigmatism of 1 diopter or greater. Compared to an aspheric monofocal IOL, the lens provides improved intermediate and near visual acuity, while maintaining comparable distance visual acuity.

3. CLINICAL HYPOTHESIS

The rate of bothersome visual symptom items

for the

Symfony Toric IOL higher-cylinder group will be compared to the rate for the lower-cylinder group. The bothersome visual symptom items of interest are halos, glare, and starbursts.

4. STUDY DESIGN

This study is a prospective, multicenter, bilateral, non-randomized, open-label, comparative, 6-month clinical study conducted at up to 50 sites in the USA. Subjects who meet the inclusion/exclusion criteria will be bilaterally implanted with Symfony IOLs, with either 1) Model ZXT300 or ZXT375 IOLs (higher-cylinder group), or 2) control Model ZXT150 (lower-cylinder control group) IOL, implanted in at least one eye, according to the TECNIS Symfony Toric IOL calculator. The fellow eye will be allowed to have any Symfony IOL implanted, according to the TECNIS Symfony Toric IOL calculator, provided it is the same or a lower toric power as the primary eye. The eye with the highest toric power IOL will determine the model group.

JUSTIFICATION OF STUDY DESIGN

5. ACROYNYMS

The following acronyms are used throughout the document:

- UCDVA: uncorrected distance visual acuity
- BCDVA: best corrected distance visual acuity
- D: diopters

6. STUDY OBJECTIVES AND ENDPOINTS

The objective of this post-approval study is to evaluate the rate of bothersome visual symptoms

at 6 months for the Symfony Toric IOLs with approximately 2.0 D or more of cylinder correction at the corneal plane (Models ZXT300 and ZXT375) in a larger population in clinical practice compared to the control IOL (Symfony Toric Model ZXT150 IOL), and to ensure the continued safety of the approved devices.

Study endpoints will be evaluated at 6 months postoperatively.

6.1 **PRIMARY ENDPOINT:**

The primary co-endpoints are the rate of bothersome visual symptoms and the rate of difficulty with an activity due to the symptoms at 6 months postoperative.

The rate of difficulty with an activity due to the symptoms is determined by the percentage of subjects who respond "Yes" to the question "Is there anything you have a lot of difficulty with, or do not do, because of (visual symptom) at 6 months postoperative.

The frequency and proportion of subjects reporting one or more of these items

via PRVSQ questionnaire will be used to

determine the primary endpoint. This rate will be calculated for the higher-cylinder (ZXT300 and ZXT375) and lower-cylinder (ZXT150) groups.

6.2 OTHER ENDPOINTS:

- Other questionnaire responses, such as rates of degree of bother
- Rates of IOL repositioning procedures (secondary surgical intervention) due to IOL misalignment
- Rate of explants related to visual symptoms
- Rates of other adverse events
- Monocular uncorrected distance visual acuity
- Monocular best corrected distance visual acuity

- Mean percent reduction in absolute cylinder
- Mean refractive cylinder and mean refractive cylinder compared to preoperatively-predicted cylinder
- Mean spherical equivalent and mean spherical equivalent compared to preoperatively-predicted spherical equivalent
- Percent of eyes with absolute cylinder within 0.50 D and within 1.00 D of preoperatively-predicted cylinder
- Percent of eyes with spherical equivalent within 0.50 D and within 1.00 D of preoperatively-predicted spherical equivalent
- Rates of medical and/or lens findings

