- Endophthalmitis/Intraocular infection
- Hypopyon
- Hyphema
- Lens dislocation
- Cystoid macular edema
- Mechanical pupillary block
- Rhegmatogenous retinal detachment/tear
- Persistent corneal edema
- Persistent iritis/uveitis
- Toxic anterior segment syndrome (TASS)
- Persistent elevated IOP requiring treatment

- Tilt, decentration, residual refractive error or axis misalignment resulting in secondary surgical intervention (e.g., repositioning)
- Visual symptoms requiring secondary surgical intervention
- Residual refractive error resulting in a secondary surgical intervention
- Residual lens remnants resulting in a secondary surgical intervention

Unanticipated Adverse Device Effect (UADE)/Unanticipated Serious Adverse Device Effect (USADE)

Any UADE (USA 21CFR 812.3(s)) or USADE (ISO 14155) is defined as any serious adverse effect on health or safety or any life-threatening problem or death caused by, or associated with, a device, if that effect, problem, or death was not previously identified in nature, severity, or degree of incidence in the investigational plan (i.e., this protocol), application (including a supplementary plan or application), or risk assessment, or any other unanticipated serious problem associated with a device that relates to the rights, safety, or welfare of subjects.

An SAE/ADE form will be completed by the investigative site for any UADE or USADE.

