21.3 ADDITIONAL ENDPOINTS

The frequency and proportion of subjects with each response will be reported for the individual visual symptom items for overall and with and without correction.

The frequency and proportion achieving each acuity level will be reported for monocular visual acuity.

[figure not shown]
Descriptive statistics will be reported for mean percent reduction in cylinder, refractive cylinder, cylinder vs preoperatively-predicted cylinder, spherical equivalent and spherical equivalent vs preoperatively-predicted spherical equivalent. The frequency and proportion of eyes within 0.50 D and within 1.00 D of the preoperatively-predicted values will be reported for refractive cylinder and spherical equivalent. Percent reduction in cylinder will be calculated for each eye using the following formula:

100*((Postop Ref. Cyl. - Preop K. Cyl.)/(Target Ref. Cyl. - Preop K. Cyl.)) Key: Ref. Cyl.=absolute refractive cylinder; K. Cyl.=keratometric cylinder;

[figure not shown]
Refractive data will be referred to the corneal plane prior to determining percent reduction in cylinder.

Enrollment data, demographic data, subject accountability data and operative complications/procedures will be reported using descriptive statistics. Visual symptom findings, adverse events and other key data will be reported at 1 year for subjects who experienced a repositioning procedure during the study or who were reported with bothersome visual symptoms at the 6-month visit.

The frequency and proportion of primary and fellow eyes with medical/lens findings will also be reported. In addition, rates of IOL repositioning procedures (secondary surgical intervention) due to IOL misalignment, rates of explants related to visual symptoms, rates of refractive procedures performed during the study period, and other adverse events will be reported.

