## 5.4 SAFETY ENDPOINTS/MEDICAL/LENS FINDINGS

The frequency and proportion of medical and lens findings will be reported for primary and fellow eyes of toric subjects. The frequency and proportion of adverse events at any time postoperative will also be reported.

A listing of serious adverse event or device-related events will also be provided for all subjects. Rates of IOL repositioning procedures (secondary surgical intervention) due to IOL misalignments, rates of explants due to visual symptoms will also be reported.

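### The two named lens-procedure rates depend on the cause an unmasked investigator records, and overlapping event categories mean each rate can be understated

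*Protocol*

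**What the plan says.** Protocol 6.2 lists two lens-procedure rates, each tied to a cause: "Rates of IOL repositioning procedures (secondary surgical intervention) due to IOL misalignment" and "Rate of explants related to visual symptoms". The same list ends its safety items with a catch-all, "Rates of other adverse events". The synopsis and Protocol 21.3 carry the same two limits, and Protocol 21.3 adds "rates of refractive procedures performed during the study period, and other adverse events will be reported".

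SAP 5.4 follows suit: "Rates of IOL repositioning procedures (secondary surgical intervention) due to IOL misalignments, rates of explants due to visual symptoms will also be reported". It also provides for adverse-event frequencies at any postoperative time and a listing of serious or device-related events. SAP 2.1 says adverse-event data are reported separately by group.

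Protocol 12.1 lists anticipated serious events. Three lines could describe one procedure on a study lens:

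- "Tilt, decentration, residual refractive error or axis misalignment resulting in secondary surgical intervention (e.g., repositioning"
- "Residual refractive error resulting in a secondary surgical intervention"
- "Visual symptoms requiring secondary surgical intervention"

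**The concern.** Each named rate counts a procedure only if it was recorded with one particular cause. Rotation of a toric lens shows itself as residual cylinder; Protocol 18 itself says that rotation reduces the astigmatic correction. One physical event can therefore fairly be described as misalignment or as residual refractive error. Only the first description plainly enters the repositioning rate. An explant for any reason other than visual symptoms is outside the explant rate by definition.

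At stake is the second half of the study objective, continued safety of the approved lenses. A reader who wants to know how often a study lens was moved or removed in each group would look to these two rates, and neither answers that question. The explant limit has a further consequence. Under Protocol 11.8 a subject whose study lens is removed is discontinued, while the primary analysis population needs 6-month data. A subject explanted before then for another reason can be absent from both the primary endpoints and the named explant rate.

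**Working it through.** The plan states no rate, margin or precision for repositioning or explant, so there is no figure of its own to reproduce. The check has four parts.

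**1. Do the categories overlap?** In Protocol 12.1, residual refractive error shares a line with tilt, decentration and axis misalignment, and also has a line of its own. Visual symptoms leading to surgery form a third. The visible text gives no order of precedence and no adjudication of cause. The postoperative data list in Protocol 11.6 covers refraction, keratometry and slit-lamp findings but shows no measurement of lens axis that would settle the matter. Protocol 4 describes the study as open-label, so whoever records the cause knows the lens model.

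**2. How far could the rate move?** The inputs are 240 evaluable subjects per group and 5% loss (Protocol 21.5), so implanted subjects per group = 240/0.95 = 252.6, rounded up to 253. Assume 6 rotation-driven repositionings, at most one per subject. Neither this count nor the recoding share is in the documents.

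| Recorded elsewhere | Named rate | Exact 95% CI |
|---|---|---|
| 0 | 6/253 = 2.4% | 0.9% to 5.1% |
| 2 | 4/253 = 1.6% | 0.4% to 4.0% |
| 3 | 3/253 = 1.2% | 0.2% to 3.4% |

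The estimate can halve, but with so few events the intervals overlap heavily.

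**3. Does it differ by group?** For an otherwise full correction, residual cylinder after rotation by θ is about 2 × C × sin θ, where C is the corneal-plane cylinder in Protocol Table 1. At 30° the factor 2 × sin 30° is 1.00, which agrees with the 30° statement in Protocol 18. At 10°:

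- ZXT150: 2 × 1.03 × 0.1736 = 0.36 D
- ZXT300: 2 × 2.06 × 0.1736 = 0.72 D
- ZXT375: 2 × 2.57 × 0.1736 = 0.89 D

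The same rotation thus leaves 2.0 to 2.5 times as much cylinder in the higher-cylinder lenses. That gives a reason to expect more procedures there. It says nothing about the share recorded under another cause. With named rate = true rate × (1 − share recorded elsewhere), and assumed true rates of 2% (higher) and 1% (lower):

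| Share elsewhere, higher / lower | Named rates | Ratio |
|---|---|---|
| 0% / 0% | 2.0% v 1.0% | 2.0 |
| 50% / 50% | 1.0% v 0.5% | 2.0 |
| 50% / 0% | 1.0% v 1.0% | 1.0 |
| 25% / 50% | 1.5% v 0.5% | 3.0 |

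The contrast can survive, vanish or grow, depending on shares the documents do not give.

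**4. Is cause treated consistently elsewhere?** No. The 1-year visit is triggered only by a repositioning for misalignment (synopsis, Protocol 11.1 and 11.6, SAP 1), apart from the separate symptom trigger. The 1-year reporting set in Protocol 21.3 includes subjects with a repositioning, without a cause limit, and the supplementary analysis in Protocol 21.1 likewise refers to any repositioning or lens removal. A subject repositioned for another recorded cause could be due in the 1-year report with no 1-year visit required.

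**The case against.** The strongest reply is that nothing is lost. Interventions for misalignment, residual refractive error and visual symptoms are all anticipated serious events. They go on the SAE/ADE form, are notified within 24 hours, and are reviewed by the medical monitor. They would appear among other adverse events and in the SAP listing. This stands: a reader might infer that such procedures vanish from safety reporting, and the documents show otherwise. What remains is that no prespecified row gives the total, so it would have to be rebuilt from several places. SAP 5.4 as visible also omits the refractive-procedure rate promised in Protocol 21.3.

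A second reply is that the list in Protocol 12.1 is for reporting to the sponsor and is not shown to be the scheme that fills the numerator. Moreover, repositioning is the example given only on the line that includes axis misalignment. This also has force: many repositionings would probably be filed there anyway. It does not help with explants, nor does it say how a cause is chosen from within that combined line.

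A third reply is that redacted text, the table listing or the case report forms may hold an attribution rule or an all-cause row. That cannot be excluded.

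Finally, a reader might infer from the rotation arithmetic that events drop out more readily in the higher-cylinder group. The documents do not support this. A larger residual cylinder could equally make rotation the more obvious cause to record.

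**Conclusion.** The point holds in a limited form. Both named rates rest on attribution by an investigator who knows the lens, the listed categories overlap, and no rule for resolving the overlap is visible. Each rate can therefore understate how often a study lens was repositioned or removed. The size is unknown: the fall from 2.4% to 1.6% or 1.2% rests wholly on assumed counts. No direction of bias between groups is shown. Severity is minor, because these are descriptive, non-primary endpoints with no test, margin or decision rule, and the events are reported elsewhere. The mismatch between the 1-year visit trigger and the 1-year reporting set is an inconsistency in the text itself and does not depend on any of these assumptions.

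**What to change.** In SAP 5.4, and in Protocol 6.2 and 21.3 when next amended, report by group with 95% CIs:

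- (a) all secondary repositionings of a study lens, whatever the recorded reason;
- (b) all explants or exchanges of a study lens, whatever the recorded reason.

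Beneath each total, break the count down by reason (misalignment, residual refractive error, tilt or decentration, visual symptoms, other), keeping the two current cause-specific rates as sub-rows. One sentence should say how the reason is assigned when more than one applies, so that the sub-rows can be read. Separately, reconcile the wording on 1-year follow-up between the synopsis, Protocol 11.1, 11.6 and 21.3, and SAP 1.

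The cost is a few table rows and a possibly slightly higher headline rate. The SAE/ADE form already captures these events, so no new data collection is apparent. Changing the SAP first avoids a protocol amendment, with its FDA and IRB approval, for this point alone.
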